9.7.5 Body Weight

Body weight will be summarized at Baseline (Screening), Day 168 and early termination. Baseline will be defined as the last assessment prior to the first dose.

Summary tabulations of weight (n, mean, standard deviation, median, minimum, and maximum) for baseline, each scheduled visit, and change from baseline will be provided for the safety analysis set by treatment group.

9.7.6 Columbia-Suicide Severity Rating Scale

The C-SSRS is a semi-structured interview that captures the occurrence, severity, and frequency of suicide-related thoughts and behaviors during the assessment period. The interview includes definitions and suggested questions to solicit the type of information needed to determine if a suicide-related thought or behavior occurred.

The interview measures presence of suicidality, specifically suicidal ideation (including intensity of ideation) and suicidal behavior.

The C-SSRS must be performed by an individual who is trained in its use and certified to perform the assessment.

Two versions of the C-SSRS are used in this study: the "Baseline/Screening" version, and the "Since Last Visit" version.

The C-SSRS "Baseline" version is completed at Screening (Visit 1), and C-SSRS "Since Last Visit" version is completed at all subsequent visits.

All C-SSRS data collected on the eCRF will be included in the data listings. The number and percent of subjects reporting "Yes" for each of the 5 questions to suicidal ideation and 6 questions about suicidal behavior will be summarized by treatment group and visit. In addition, for suicidal behavior, the total number of actual attempts, total number of interrupted attempts and total number of aborted attempts will be summarized (n, mean, standard deviation, median, minimum and maximum) by treatment group and visit.

9.7.7 Epworth Sleepiness Scale

There are eight situations to the ESS. All data from the ESS eCRF will be included in the data listings. The total score from the ESS will be summarized (n, mean, standard deviation, median, minimum and maximum) by treatment group and visit and change from baseline. The total score is derived as the sum of eight situations. If one or more of the eight situations are missing at a given visit for a subject, the total score will not be derived. All data collected on the ESS will be included in the data listings.

9.7.8 Episodes of Sudden Onset of Sleep

The sudden onset of sleep will be recorded at baseline and Weeks 0, 2, 6, 12, 18 and 24 as well as Early Termination. The responses to "did the subject experience any sudden onset of sleep" will be summarized by count and percentages by treatment group and visit. Shift from baseline to each scheduled visit will be summarized for the safety analysis set by treatment group for each sudden onset of sleep questions. All data collected on the episodes of sudden onset of sleep will be included in the data listings.

9.7.9 Modified Minnesota Impulsive Disorders Interview

mMIDI is reported at Weeks 6, 12, 18, 24 and early termination. For the mMIDI module scores and total score, if a question is not answered with a module, then that given module score and the total score will not be determined for the subject at the visit.

CONFIDENTIAL

The mMIDI modules are Buying Disorder, Compulsive Gambling, Compulsive Sexual Behavior, Compulsive Eating, and Punding Behavior. The number and percent of subjects in each module with a positive/negative indication for the module will be reported. In addition, shift from baseline to each scheduled visit will be summarized for the safety analysis set by treatment group

All data collected on the mMIDI will be included in the data listings.

9.7.10 ECG

ECG data will be summarized for the following visits: Screening, Weeks 0, 2, 6, 12, 18, 24 and early termination. Descriptive statistics (n, mean, standard deviation, median, minimum and maximum) of each parameter (HR, PR, RR, QRS, QT, QTcB and QTcF) by treatment group will be displayed for the observed value and change from baseline at each scheduled listed above for the safety analysis set.

The number and percentage of subjects with maximum post-dose QT/QTcB/QTcF interval within the following ranges will be summarized by treatment group:

- ≤450 msec
- >450 msec and ≤480 msec
- >480 msec and ≤ 500 msec
- >500 msec.

In addition the number and percentage of subjects with maximum change from Baseline in QT/QTcB/QTcF interval within the following ranges will be summarized by treatment group:

- ≤30 msec
- >30 msec
- ≤60 msec, and >60 msec.

ECG findings will be classified as normal or abnormal, with abnormal values further classified according to clinical significance (yes/no). The percentage of subjects with clinically significant findings and clinically significant treatment-emergent findings will be summarized by treatment group for each visit.

All ECG data collected will be included in the data listings

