6.2.35 Post-Early Termination Safety Follow-Up Visit

After Early Termination, the patient will also be asked to return for a Safety Follow-Up Visit to be scheduled 28 days after the last dose of IMP. If an Early Termination Visit took place 28 or more days after the last dose of IMP, this visit will not be conducted.

Note: Confirm the arrangement for laboratory sample pick-up on the day of the visit with the courier (see Central Laboratory Procedures Manual).

- 1. Assess AEs by asking open-ended queries and record the assessments.
- 2. Record concomitant medication use; assess and record any changes to anti-PD medication dose or regimen.
- 3. Obtain and record BP and pulse measurements after at least 5 minutes supine rest and again after standing for approximately 1 and 3 minutes.
- 4. Obtain 12-lead ECG and ensure the ECG is collected at a time when the patient is not experiencing dyskinesia that would interfere with an adequate recording. Assess any changes from Baseline for clinical significance.
 - Part B only: Obtain weight.
- 5. Have the patient complete the following self-assessment questionnaire:
 - Parts A and B: ESS.
- 6. Administer the following assessments (may be done anytime during visit):
 - Parts A and B: mMIDI.
 - Parts A and B: C-SSRS.
 - Part A only: Assessment for episodes of sudden onset of sleep.
- 7. Obtain samples for the following laboratory tests and record the date and time of collection:
 - a. Hematology and chemistry (inclusive of liver function tests).
 - b. TSH, free T3, and free T4.
 - c. Urine sample for urinalysis.
 - d. Verify method of contraception has not changed since the previous visit. For females of childbearing potential: urine pregnancy test.

8. Perform physical and neurological examination, and assess any changes from Baseline for clinical significance.

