5.13 Treatment-Emergent Adverse Events (TEAEs)

TEAEs are those which first occur or increase in severity or relationship to study drug after the first dose of study drug through the Post-dose Follow-up (28 ± 3 days after end of treatment). In reality all AEs which change in severity or relationship to study drug are assigned a new start date and captured as a new record. Should the day of the AE be "unknown" and the AE in question occurs in the same month or a following month as the date of first dose, the AE will be considered treatment emergent. Should the month of the AE be "unknown" and the AE in question occurs in the same year or a following year as the date of first dose, the AE will be considered treatment emergent. Should the start date be missing then the AE will be considered treatment emergent.

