9.7.4 Systolic and Diastolic Blood Pressure and Pulse Rate

Systolic and diastolic blood pressure and pulse rate will be measured in both the supine and standing positions. The scheduled visits that will be summarized are Weeks 2, 6, 12, 18, 24 and early termination. In addition, on Day 1, there are to be 3 measurements for both supine and standing, respectively, at least 10 minutes apart. Orthostatic change (difference between standing and supine) in systolic and diastolic blood pressure and pulse rate will be derived. The baseline value for the supine and standing blood pressure and pulse rate will be the average of the 3 measurements taken at least 10 minutes apart prior to first dose on Day 1, as defined in **Section 5**.

Summary tabulations of the systolic and diastolic blood pressure and pulse rate in both standing and supine positions as well as the orthostatic change (n, mean, standard deviation, median, minimum, and maximum) for baseline, each scheduled visit, and change from baseline will be

provided for the safety analysis set by treatment group. In addition, the placebo corrected mean change from baseline (tozadenant treatment group mean change from baseline minus placebo mean change from baseline) for systolic and diastolic blood pressure and pulse rate in both standing and supine positions as well as the orthostatic change will be summarized (n, mean, standard deviation, median, minimum, and maximum) for the safety analysis set by treatment group.

CONFIDENTIAL

At each scheduled post-baseline visit and time point (Weeks 2, 6, 12, 18, 24 and early termination), the number and percent of subjects meeting each abnormal criteria displayed below will be summarized by treatment group.

- Supine and standing systolic blood pressure
 - ≥160 mmHg
 - < 100 mmHg

 - ≥20 mmHg increase from baseline
 - ≥20 mmHg decrease from baseline
 - ≥40 mmHg increase from baseline
 - ≥40 mmHg decrease from baseline
- Supine and standing diastolic blood pressure
 - ≥100 mmHg
 - <50 mmHg
 - ≥10 mmHg increase from baseline
 - ≥10 mmHg decrease from baseline
 - ≥20 mmHg increase from baseline
 - ≥20 mmHg decrease from baseline
- Supine and Standing Pulse rate
 - ≥120 bpm
 - <48 bpm
 - ≥30 bpm increase from baseline
 - ≥30 bpm decrease from baseline
- Orthostatic change ≥20 mmHg increase from baseline for systolic blood pressure and diastolic blood pressure
- Orthostatic change ≥20 mmHg decrease from baseline for systolic blood pressure and diastolic blood pressure

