9.7.11 Physical and Neurological Examinations

Physical and Neurological examinations are performed at Screening, week 24 and early termination. The number and percentage of subjects with normal/abnormal findings will be summarized by body system/neurological area, treatment group and visit. All abnormalities will be included in the data listings.

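### Five SAP safety sections name visit lists that end at early termination and omit the Part A 28-day Safety Follow-Up (A99), where the protocol collects all five assessments

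*SAP*

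**What the plan says.** For patients who stop early in Part A, Protocol 6.2.35 says that "the patient will also be asked to return for a Safety Follow-Up Visit to be scheduled 28 days after the last dose of IMP". Table 1 gives this visit the code A99 and a window of ± 3 days. Both places call for supine and standing blood pressure and pulse, a 12-lead ECG, the mMIDI, the sudden-onset-of-sleep assessment and a physical and neurological examination. Protocol 11.5.1 says that safety data will be described, as observed values and as change from Baseline, at every time point measured.

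The SAP names visits as follows:

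- 9.7.4, blood pressure and pulse: "The scheduled visits that will be summarized are Weeks 2, 6, 12, 18, 24 and early termination". The same list is repeated for the counts of abnormal values.
- 9.7.8, sudden-sleep episodes: "The sudden onset of sleep will be recorded at baseline and Weeks 0, 2, 6, 12, 18 and 24 as well as Early Termination".
- 9.7.9, mMIDI: "mMIDI is reported at Weeks 6, 12, 18, 24 and early termination".
- 9.7.10, ECG: "ECG data will be summarized for the following visits: Screening, Weeks 0, 2, 6, 12, 18, 24 and early termination".
- 9.7.11, examinations: "Physical and Neurological examinations are performed at Screening, week 24 and early termination".

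SAP 5.13 defines treatment-emergent adverse events as those that begin or worsen "after the first dose of study drug through the Post-dose Follow-up", which it places 28 ± 3 days after the end of treatment.

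**The concern.** The SAP treats the 28 days after the last dose as part of the safety period when it counts adverse events, but its tables for five objective or structured assessments stop before the visit that closes that period. Patients who reach A99 are those who left Part A early, and they include anyone withdrawn under the QTcF or blood pressure criteria in Protocol 4.3.2. For these patients A99 is a scheduled look after drug has been stopped. If it is not tabulated, a reader of the by-arm tables sees the values up to termination and not the follow-up values.

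Two of the sections raise a further problem. SAP 9.7.8 and 9.7.11 describe when the assessment is recorded or performed, and both lists lack a visit that the protocol schedule contains. They need correcting whatever is decided about tables.

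**Working it through.** **Schedule against SAP.** The check is a comparison of visit lists. In the copy reviewed, the follow-up column of the SAP's own schedule (Table 3-1) is cut off, so the protocol's Table 1 and Section 6.2.35 are used.

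| Assessment | At A99 in the protocol | Visits named in the SAP end at | Where A99 data go as written |
|---|---|---|---|
| Blood pressure, pulse | Yes | Early termination (9.7.4) | Listing |
| Sudden onset of sleep | Yes (Part A) | Early termination (9.7.8) | Listing |
| mMIDI | Yes | Early termination (9.7.9) | Listing |
| 12-lead ECG | Yes | Early termination (9.7.10) | Listing |
| Physical and neurological examination | Yes | Early termination (9.7.11) | Listing of abnormal findings only |

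All five assessments are collected at A99, and all five SAP sections omit it. In the last row, a normal A99 examination would appear in neither a table nor a listing.

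**Assessments that are not affected.** SAP 9.7.3 summarises laboratory data at each scheduled visit in the schedule table. SAP 9.7.6 (C-SSRS) and 9.7.7 (ESS) summarise by visit. None of the three names a restricted list. Weight is not measured at the Part A follow-up (6.2.35 asks for it in Part B only).

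**How many patients.** Protocol 3.1.2 expects 80% of 450 randomised patients to complete Part A and continue:

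- Continuing: 450 × 0.80 = 360, which matches the stated figure of about 360.
- Not continuing: 450 − 360 = 90.
- Per arm, assuming equal non-continuation: 90 / 3 = 30.

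The 90 can include patients who withdraw at Week 24, because Protocol 6.2.18 treats that visit as an early termination with a follow-up. It is a ceiling: A99 is waived when the termination visit falls 28 or more days after the last dose, and some patients will not return.

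The documents give no range for non-continuation. For an assumed 10% to 30%, the number per arm is 150 × 0.10 = 15 to 150 × 0.30 = 45.

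**What such a row can show.** With no events in n patients, the one-sided 95% upper bound is 1 − 0.05^(1/n):

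- n = 15: 18.1%
- n = 30: 9.5%
- n = 45: 6.4%

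The row is therefore descriptive. No sample size, power or alpha figure changes.

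**The case against.** The case against is substantial, and most of it limits the point.

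- **The lists may not be closed.** SAP 9.7.9 omits Screening yet promises shifts from baseline, and 9.7.8 and 9.7.9 speak of shifts to each scheduled visit. Table shells are deferred, so the final rows cannot be seen. This stands as far as it goes: the omission may be loose drafting. But each section names its visits, and a programmer following the text would leave A99 out.
- **A reader might infer that all off-drug data are lost.** The documents do not support this. The early termination visit should be on drug if possible, but it may come later, even 28 or more days after the last dose. Some off-drug values therefore sit in the tabulated early-termination row, and A99 is not the only scheduled Part A visit at which they can arise. That mixing is itself a reason to keep A99 in a row of its own.
- **A reader might extend the point to liver or neutrophil recovery.** That does not hold. Laboratory tables have no restricted list, and Protocol 4.3.2 requires weekly haematology after a neutrophil withdrawal.
- **New clinically significant examination findings are not lost.** Protocol 11.5.1 records them as adverse events, and the adverse event window covers A99, so they are counted by arm.
- **SAP 9.7.11 does not say that examinations happen only at its three visits.** Correct; its list is incomplete rather than exclusive.
- **The subset is selected after randomisation, partly by the effects of treatment.** Completers go straight to open-label drug, and their off-drug visit at Week 80 is left to the Part B SAP. An A99 row cannot give a randomised comparison of recovery. This stands in full and fixes the use of the row as description. It does not explain why laboratory, ESS and C-SSRS data from the same visit can be tabulated while ECG and blood pressure are left out.

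**Conclusion.** The point holds as a minor mismatch between the SAP and the protocol. Five assessments collected at A99 are missing from the visits that the SAP names for them. This departs from Protocol 11.5.1 and is uneven with the SAP's own adverse event window. At most about 90 of 450 patients are concerned, about 30 per arm if non-continuation is equal across arms and matches the planned 20%, and fewer where the visit is waived or missed. For four of the five the data remain in listings; for examinations only abnormal findings do.

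A related ambiguity remains. SAP 9.7.10 groups patients by maximum post-dose QT, QTcB and QTcF without saying whether A99 ECGs count. Either answer is workable, but a maximum cannot show recovery, so the categories do not replace a follow-up row.

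A reader might also want a count of patients whose values returned within a 4.3.2 limit by A99. Those criteria do not lend themselves to it: QTcF must be consistently raised and blood pressure raised at two consecutive visits, so classifying patients on a single last value would not match them. The efficacy conclusions are untouched.

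**What to change.** 1. In SAP 9.7.4, 9.7.8, 9.7.9, 9.7.10 and 9.7.11, add the Part A Safety Follow-Up (A99) as a separate post-treatment row by arm, not pooled with on-treatment visits. Show the number of patients contributing, and label the row as descriptive in patients who stopped early.
2. Correct the visit lists in 9.7.8 and 9.7.11 so that they match protocol Table 1 and Section 6.2.35.
3. State in 9.7.10 whether A99 ECGs enter the maximum post-dose QT and QTc categories.

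The cost is SAP wording and one row in each affected table. The data are already collected, and nothing in the visit schedule, sample size or error control changes.

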9.7.11 Physical and Neurological Examinations

Physical and Neurological examinations are performed at Screening, week 24 and early termination. The number and percentage of subjects with normal/abnormal findings will be summarized by body system/neurological area, treatment group and visit. All abnormalities will be included in the data listings.

9.8 Other Exploratory Analyses

9.8.1 Efficacy Sub-group Analyses

The change from baseline to Week 24 in the number of hours per day spent in the OFF state while awake will be assessed in the following sub-groups:

- Caffeine intake at baseline: no caffeine vs. 1 500 mg/day caffeine vs. > 500 mg/day caffeine.
- Levodopa dose at baseline
- Levodopa equivalent dose at baseline

The MMRM model described in **Section 9.6.1** will be used in all sub-group analyses with the specific subgroup included as an additional covariate. The analysis will be performed in the mITT analysis set.

The assumption of the absence of a treatment by sub-group interaction will be tested using a liberal significance level of 15%. If an interaction is suggested, the results regarding treatment effects will be summarized descriptively for each sub-group and treatment to explore the source of the interaction.

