9.6.1 Primary Variable

The primary variable, change from baseline to Week 24 in the 3-day average of total awake time in hours per day spent in the OFF state, will be summarized and analyzed in the mITT and repeated in the PPS.

Descriptive statistics (n, mean, standard deviation, median, minimum, and maximum) will be used to summarize results for OFF time by treatment group and week. Only valid diaries (see **Section 5.3**) post baseline are included in the analyses.

At Week 24, a plot of the cumulative distribution (cumulative of subjects) of average change from baseline in OFF state in hours will be displayed.

The null and alternative hypotheses are as follows:

 H_0 : $\mu_a - \mu_p = 0$

 H_1 : $\mu_a - \mu_p \neq 0$

where μ_a and μ_p are the mean changes from baseline to Week 24 in the 3-day average of total awake time in hours per day spent in the OFF state for the tozadenant and placebo groups, respectively.

The primary analysis will be performed on the change from baseline OFF hours using a mixed model repeated measures ANCOVA that includes fixed terms for country/region, treatment group, week (categorical: 2, 6 12, 18 and 24), interaction between treatment group and week, baseline number of hours of OFF time (covariate) and random effect for subject. This model will allow for estimation of treatment effects (each dose regimen of tozadenant vs placebo) separately at each week as well as averaged across weeks.

Restricted Maximum Likelihood (ReML) estimation will be used with an unstructured covariance structure to model the within-patient error and the Kenward-Roger approximation to estimate the

degrees of freedom. If the model does not converge using the unstructured covariance structure, the AR(1) structure may be considered.

MMRM model assumptions including constant variance, normality of errors and normality of random intercepts will be assessed by residual plots.

CONFIDENTIAL

A test of the null hypothesis of the equality of the adjusted group means in the tozadenant and placebo groups will be performed for each dose regimen of tozadenant using a significance level of 5% (two tailed). Treatment differences will be summarized by least squares means (standard errors) and corresponding 95% confidence intervals.

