9.6.5 Exploratory Variables

The exploratory variables will be summarized by descriptive statistics by treatment group in the mITT. No statistical analyses are planned. The list of variables includes the change from Baseline to Week 24 (where applicable) for the following:

- 1. Number of hours per day spent in the asleep state.
- 2. Dyskinesia as measured by questions 32, 33 and 34 of UPDRS Part IV.
- 3. Falls as measured by question 13 on UPDRS Part II.
- 4. Responder analysis of number (%) of patients with ≥ 1.0 h improvement in OFF time (evaluated at Week 24).
- 5. Responder analysis of number (%) of patients with ≥ 2.0 h improvement in OFF time (evaluated at Week 24).
- 6. Percent change in total levodopa equivalent dose.
- 7. Percent change in the number of hours per day spent in OFF state.
- 8. Percent change in the number of hours per day spent in ON state without troublesome dyskinesia.
- 9. Percent change in the number of hours per day spent in ON state with troublesome dyskinesia.
- 10. Scales for Outcomes in Parkinson's Disease-cognition (SCOPA-cog) score.
- 11. Fall questionnaire score.
- 12. Number of hours per day spent in the OFF state in the sub-population of subjects taking levodopa and only one additional concomitant anti-PD medication.
- 13. Number of hours per day spent in the OFF state in the sub-population of subjects taking levodopa and two additional concomitant anti-PD medications.
- 14. Number of hours per day spent in the OFF state in the sub-population of subjects taking levodopa and three additional concomitant anti-PD medications.

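### SAP 9.8.1 makes its subgroup results conditional on a 15% interaction test, at an unnamed visit, that can miss a 0.9 h Week 24 difference nearly half the time

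*SAP*

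**What the plan says.** SAP 9.8.1 fixes the quantity of interest: "The change from baseline to Week 24 in the number of hours per day spent in the OFF state while awake will be assessed" by caffeine intake (three levels given), by baseline levodopa dose and by baseline levodopa-equivalent dose (no levels given for either). It uses the repeated-measures model of SAP 9.6.1 "with the specific subgroup included as an additional covariate". That base model contains week, "interaction between treatment group and week, baseline number of hours of OFF time (covariate) and random effect for subject", besides country/region and treatment. SAP 9.8.1 names no subgroup-by-week or treatment-by-subgroup-by-week term.

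On the interaction it says: "The assumption of the absence of a treatment by sub-group interaction will be tested using a liberal significance level of 15" per cent. No visit is attached to that test. The next sentence is the only one that describes results per subgroup, and it begins with a condition: "If an interaction is suggested, the results regarding treatment effects will be summarized descriptively for each sub-group and treatment to explore the source".

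SAP 9.6.5 separately lists OFF time by number of added anti-PD drugs, summarised descriptively with no condition. Items 12 and 13 cover one and two added drugs. Item 14 covers the "sub-population of subjects taking levodopa and three additional concomitant anti-PD medications". Inclusion criterion 7 in Protocol 4.1 names five kinds of added treatment, with a minimum of one and no maximum.

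**The concern.** Interaction tests have much less power than the main comparison for which a trial is sized. If subgroup estimates appear only after such a test is passed, the reader of the report cannot tell a subgroup effect that is truly uniform from one that was imprecisely measured. An estimate with its interval answers that question; a non-significant p-value does not.

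The unnamed visit adds to this. The target is Week 24, but the model spans Weeks 2 to 24, and a treatment-by-subgroup term can be tested at one visit or as one effect common to all visits. These are different questions with different power, and the choice would be made later.

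What is at stake is the usefulness of the exploratory subgroup results. The primary test, the key secondary tests, alpha and the sample size are not involved.

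**Working it through.** **Inputs from the documents.** SAP 3.2: 150 per arm, difference 0.9 h, SD 2.6 h, two-sided alpha 0.05, stated power 85%. SAP 9.8.1: interaction alpha 0.15, taken as two-sided because the SAP does not say. Protocol 3.1.2: 80% expected to complete Part A, so 0.8 × 150 = 120 per arm at Week 24.

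**Assumptions.** Subgroup shares, size of the interaction (the difference between subgroup treatment effects) and between-visit correlation rho are not in the documents.

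**Step 1: reproduce the plan's figure.** SE = 2.6 × √(2/150) = 0.300. 0.9/0.300 = 3.00, and 3.00 − 1.96 = 1.04. Power = 85.0% (84.8% by noncentral t). The stated 85% is confirmed.

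**Step 2: Week 24 interaction, one dose against placebo, equal halves.** There are 75 patients per arm in each half.
- SE = 2.6 × √(2/75 + 2/75) = 0.600.
- 0.9/0.600 = 1.50, against a critical value of 1.44. Power = 0.525 (0.524 by noncentral t).
- With 120 per arm, SE = 2.6 × √(2/60 + 2/60) = 0.671. 0.9/0.671 = 1.34. Power = 0.46.

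| Interaction | 150 per arm | 120 per arm |
|---|---|---|
| 0.45 h | 26% | 24% |
| 0.9 h | 52–53% | 46% |
| 1.35 h | 79% | 72% |
| 1.8 h | 94% | 89% |

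With a 25/75 split and 150 per arm, SE is 0.693 and power is 45% for 0.9 h and 88% for 1.8 h.

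**Step 3: caffeine as specified (three levels, three arms, 4 df), 150 per arm, same effects in both doses.** Noncentrality = Σ (cell size × squared interaction residual)/2.6².
- Effects 1.35/0.9/0.45 h, equal thirds: 50 × (6/9) × (2 × 0.45²)/6.76 = 2.00. Power is 35%.
- Same effects, split 15/70/15: 22.5 × (6/9) × (2 × 0.45²)/6.76 = 0.90. Power is 24%.
- Effects 1.8/0.9/0 h: 78% and 49% respectively.

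**Step 4: does the visit matter?** Suppose the interaction is one term common to the five visits. Its SE is then 0.600 × √((1 + 4·rho)/5), which is 0.465 at rho 0.5 and 0.523 at rho 0.7.
- Constant 0.9 h interaction: power 69% to 61%, against 53% for a Week 24 test.
- Interaction growing linearly to 0.9 h: the average is 0.9 × (2 + 6 + 12 + 18 + 24)/(24 × 5) = 0.465 h, and power is 34% to 30%.
- A simulation with about 20% dropout (400 runs per setting, rho 0.5 and 0.7) agrees. Constant: 61–70% (common term) against 48–50% (Week 24). Linear: 30% against 47–49%.

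So the visit matters, but in either direction.

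**Step 5: precision if estimates are always shown (equal halves).** The 95% half-width per subgroup is 1.96 × 2.6 × √(2/75) = 0.83 h at 150 per arm and 1.96 × 2.6 × √(2/60) = 0.93 h at 120. For the difference between subgroups it is 1.18 h and 1.32 h.

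**Step 6: item 14.** Exactly one, two and three added drugs are covered. Five kinds are permitted without a maximum, so four or more is possible and is in no group. The documents give no frequency.

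**The case against.** The section is headed as exploratory, and a liberal interaction screen followed by description is a recognised approach. SAP 9.8.1 opens by saying without condition that the endpoint will be assessed in the subgroups. It reuses a model whose treatment differences come with 95% intervals in SAP 9.6.1, and table shells are still to be written (SAP 1). The power figures in step 2 assume two halves and one dose. Caffeine has three levels, and the two levodopa factors could enter as continuous covariates. A 1.8 h interaction in equal halves is missed in only 6% to 11% of trials. Three factors tested at 15% already give a 1 − 0.85³ = 39% chance of at least one false flag if independent, so showing more estimates invites over-reading.

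Most of this limits the point and does not remove it. The opening sentence does not say what will be presented, and the only per-subgroup output described carries the condition. Step 3 shows that the caffeine test as specified has lower power than the two-halves case for a spread of the same size. The risk of over-reading is real; labelling and intervals address it better than a p-value gate.

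Three stronger readings are tempting, and the documents do not support them.
- **That the test is averaged over Weeks 2 to 24.** This is inferred from the absence of further week terms; the SAP does not state it, and SAP 9.6.1 speaks of effects both per week and across weeks. Nor is averaging always harmful: a constant interaction is found more often that way.
- **That the SAP orders estimates to be withheld.** That is a fair implication of the conditional sentence, but it is not stated.
- **That caffeine is the trial's leading effect-modification question.** It is one of three unranked factors, and no objective mentions it.

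**Conclusion.** The point holds as a modest, inexpensive improvement to an exploratory analysis. As written, a subgroup difference equal to the whole design effect (0.9 h) would pass the 15% screen at Week 24 about 53% of the time with 150 per arm, and about 46% with 120. This assumes equal halves, one dose against placebo and SD 2.6 h. For the three-level caffeine test, a 0.9 h spread would pass 24% to 35% of the time under the assumed shares. Large interactions mostly pass when the split is even.

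A reader might infer that real differences will usually go unreported. That depends on their size and the split, and the supportable statement is that sizeable ones can be left unsummarised. The visit of the test is best described as unspecified. The gap in items 12 to 14 is literal but small: those patients remain in the primary analysis if otherwise eligible for it.

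**What to change.** In SAP 9.8.1:
- State that the Week 24 tozadenant-placebo difference with its 95% CI will be reported for each subgroup and each dose, whatever the interaction p-value, and labelled exploratory. A forest plot per dose is enough.
- Take the estimates from a model that lets the subgroup effect differ by week: treatment-by-subgroup-by-week with its lower-order terms.
- Name the visit of the interaction test and treat its p-value as supportive only.
- Give levels for levodopa and levodopa-equivalent dose, since per-subgroup reporting needs them.

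Change exploratory item 14 to three or more additional anti-PD medications in SAP 4.2.3 and 9.6.5 and in the matching protocol lists (Synopsis, 2.2.4, 11.2.1.4 and 11.4.5).

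The cost is SAP text, one plot per dose and a wording change in the protocol lists. There are two downsides. There are more exploratory intervals to read, with some risk of over-reading chance differences. Also, a Week 24 estimate is less precise than a common term if the interaction is in fact constant over time.
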